Patient participation includes up to 21 days of screening, 1 year of treatment (Parts 1 and 2) or until disease progression (Part 3), and 1 month posttreatment follow-up (end-of-treatment [EOT] visit). Patients who discontinue for reasons other than PD will continue PFS follow-up every 4 weeks from the EOT visit until the occurrence of PD, death, the start of subsequent systemic antineoplastic therapy, study termination, or until 6 months after the discontinuation of study treatment, whichever occurs first. OS follow-up continues every 12 weeks from the EOT visit until death, study termination, or patient withdrawal.

The estimated time frame for study completion is

Main Criteria for Inclusion

Patients with evidence of disease progression during/after the most recent line of therapy who are in need of additional myeloma therapy as determined by the investigator and have previously received ≥ 3 prior lines of therapy.

Patients in the Part 2 expansion and Part 3 extension cohorts must have measurable disease defined as one of the following: serum M-protein \geq 500 mg/dL (\geq 0.5 g/dL); urine M-protein \geq 200 mg/24 hours; serum free light chain (FLC) assay, with involved FLC level \geq 10 mg/dL (\geq 100 mg/L). During dose escalation only, patients not meeting these criteria should, at least, have measurable bone marrow plasmacytosis (\geq 10%) and/or plasmacytoma (\geq 1 cm in diameter) detected by physical examination or imaging. Patients must have adequate organ function as determined by the following laboratory values: absolute neutrophil count (ANC) \geq 1000/mm³ (\geq 1.0×10°/L); platelets \geq 75,000/mm³ (\geq 75 × 10°/L); hemoglobin \geq 75 g/L; creatinine clearance \geq 30 mL/min (Cockcroft-Gault); total bilirubin \leq 2.0 × upper limit of normal (ULN); and alanine aminotransferase/aspartate aminotransferase (ALT/AST) \leq 3.0 × ULN.

Part 1: Until the MTD/OBD is defined, patients who have received daratumumab (or other investigational anti-CD38 antibody) for at least 5 months (steady state) require a 90-day wash-out period before receiving modakafusp alfa. For patients who have received less than 5 months of daratumumab or who have received another anti-CD38 monoclonal antibody, the necessary wash-out period needs to be discussed and approved by the sponsor. Once MTD/OBD has been confirmed, these patients can be enrolled in the trial (Parts 2 and 3)

Part 2 and Part 3: No washout from daratumumab or isatuximab is required.

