7.0 STUDY POPULATION

7.1 Inclusion Criteria

For Parts 1 and 2:

Each patient must meet all the following inclusion criteria to be enrolled in the study.

- 1. MM defined by the IMWG criteria with evidence of disease progression and:
 - a) Is in need of additional myeloma therapy as determined by the investigator.
 - b) Has previously received at least 3 lines of myeloma therapy (eg, containing an IMiD, a PI, an alkylating agent, and/or an anti-CD38 as single agents or in combination).
 - c) Is either refractory to, or intolerant of, at least 1 PI and at least 1 IMiD (see NOTE below).

For Part 3:

Each patient must meet all the following inclusion criteria to be enrolled in the study.

- 1. MM defined by the IMWG criteria with evidence of disease progression and:
 - a) Is in need of additional myeloma therapy as determined by the investigator.
 - b) Has previously received at least 3 lines of myeloma therapy.
 - c) Is refractory to at least 1 IMiD (ie, lenalidomide or pomalidomide [thalidomide excluded]), at least 1 PI (ie, bortezomib, ixazomib, or carfilzomib), and refractory to at least 1 anti-CD38 antibody (ie, daratumumab or isatuximab) and who have demonstrated disease progression during or after the last therapy (see *NOTE below). Patients who were primary refractory to all prior therapies, meaning they never achieved at least a MR with any previous treatment line, are not eligible.

*NOTE: Refractory is defined as <25% reduction in M-protein or progression of disease during treatment or within 60 days after cessation of treatment.

A line of therapy is defined as 1 or more cycles of a planned treatment program. This may consist of 1 or more planned cycles of single-agent therapy or combination therapy, as well as a sequence of treatments administered in a planned manner. A new line of therapy starts when a planned course of therapy is modified to include other treatment agents (alone or in combination) as a result of disease progression, relapse, or toxicity. A new line of therapy also starts when a planned period of observation off therapy is interrupted by a need for additional treatment for the disease (Rajkumar et al. 2011).

- 2. Aged 18 years or older.
- 3. For patients in Parts 2 and 3 only: Measurable disease defined as one of the following:
 - a) Serum M-protein $\geq 500 \text{ mg/dL}$ ($\geq 5 \text{ g/L}$).
 - b) Urine M-protein ≥200 mg/24 hours.

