- c) Serum free light chain (FLC) assay with involved FLC level ≥10 mg/dL (≥100 mg/L) provided serum FLC ratio is abnormal.
- 4. During Part 1 only, patients not meeting the above criteria for measurable disease should, at least, have measurable bone marrow plasmacytosis (≥10%) and/or plasmacytoma (≥1 cm in diameter) detected by physical examination or imaging.
- 5. ECOG performance status of ≤ 2 .
- 6. Patient has adequate organ function as determined by the following laboratory values.

Absolute neutrophil count ^a	$\geq 1000/\text{mm}^3 (\geq 1.0 \times 10^9/\text{L})$
Platelets ^a	≥75,000/mm³ (≥75×10°/L)
Hemoglobin	≥75 g/L
Creatinine clearance	≥30 mL/min (Cockcroft-Gault)
Total serum bilirubin	<2.0×ULN; an exception for patients with Gilbert's syndrome may be granted after discussion with the sponsor.
Liver transaminases (ALT/AST)	≤3.0×ULN

ALT: alanine aminotransferase; AST: aspartate aminotransferase; ULN: upper limit of the normal range.

7. Female patients who:

- Are postmenopausal for at least 2 years before the screening visit, OR
- Are surgically sterile, OR
- If they are of childbearing potential:
 - Agree to practice 1 highly effective method of contraception and 1 additional effective (barrier) method at the same time, from the time of signing the informed consent through 7 days after the last dose of study drug, OR
 - Agree to practice true abstinence, when this is in line with the preferred and usual lifestyle of the subject, from the time of signing the informed consent through 7 days after the last dose of study drug. (Periodic abstinence [eg, calendar, ovulation, symptothermal, postovulation methods], withdrawal, spermicides only, and lactational amenorrhea are not acceptable methods of contraception. Female and male condoms should not be used together.)
 - Agree not to donate an egg or eggs (ova) during the study and for 7 days after the last dose of study drug.
- 8. Male patients, even if surgically sterilized (ie, status post vasectomy), who:
 - Agree to practice effective barrier contraception during the entire study treatment period and through 7 days after the last dose of study drug, OR
 - Agree to practice true abstinence, when this is in line with the preferred and usual lifestyle of the subject. (Periodic abstinence [eg, calendar, ovulation, symptothermal,

^a Without ongoing growth factor or transfusion support for at least 1 week before Day 1.

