- s. Antiplatelet antibodies will be collected and analyzed locally until the sponsor communicates to the sites that a sufficient number of samples have been obtained to stop the collection.
- ^t Coagulation panel (prothrombin time/international normalized ratio, activated partial thromboplastin time, fibrinogen, D-Dimer) to be performed if clinically significant bleeding occurs.

Appendix A Table 12 Part 3 Extension Schedule of Events: Screening, Baseline, Cycle 1, and Cycle 2											
Study Period	Screening	Treatment Phase – Cycle 1					Treatment Phase – Cycle 2				
Cycle Day		C1D1	C1D2	C1D8	C1D15	C1D22	C2D1	C2D2	C2D8	C2D15	C2D22
Window Allowed	≤21	0	0	±2 d	±2 d	±2 d	±2 d	±0 d	±2 d	±2 d	±2 d
Informed consent ^a	X										
Eligibility criteria	X										
Demographics	X										
Medical history	X										
Prior medication and treatment history	X										
Height and weight ^b	X						X				
ECOG performance status	X						X				
12-lead ECG °	X	X		X	X		X				
Physical examination (may be symptom-directed following screening visit)	Х	X		х			X				
Vital signs ^d	X	X		X	X	X	X		X	X	X
Monitoring of concomitant medication and procedures	Recorded from signing of the ICF through 30 days after last dose of study drug or start of subsequent anticancer therapy, whichever occurs first.										
AE reporting	Recorded from signing of the ICF through 30 days after last dose of study drug or start of subsequent anticancer therapy, whichever occurs first.										
	SAEs will be reported from signing of ICF through 30 days after last dose of study drug, even if the patient starts nonprotocol therapy.										
Dosing											
Modakafusp alfa infusion ^f		X					X				
Safety Laboratory Assessments											
Chemistry i (central analysis)	X	(X)		X	X	X	X		X	X	X
Hematology ^g (central analysis)	X	(X)		X	X	X	X		X	X	X
Thyroid function tests i (local analysis)	X										
Urinalysis k(local analysis)	X						X				
Pregnancy test ¹ (local analysis)	X	X					X				

Study Period	Screening		Traatma	nt Phas	e – Cycle	1		Treatmen	t Phase _	Cycle 2	
Cycle Day	Streening	C1D1			C1D15		C2D1	C2D2	C2D8	C2D15	C2D22
Window Allowed	<21	0	0	±2 d	±2 d	±2 d	±2 d	±0 d	±2 d	±2 d	±2 d
Serology ^j (local analysis)	(X)										
Coagulation panel * (local analysis)			To be	ındertak	en if clin	ically sign	ificant ble	eding is ob	served.	 	1
Disease Assessments											
Serum M-protein m, n (central analysis)	X	(X) n		Π			X		I	Ι	

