Screening/baseline: Participants of childbearing potential must have 2 negative pregnancy tests before starting study drug.

- A urine or serum pregnancy test will be required during screening (within 10 to 14 days before start of study drug); this test must be negative.
- A urine or serum pregnancy test must be performed at baseline (within 24 hours before the start of study drug). The results from these tests must be available and negative before the first dose of study drug is administered.

On-treatment: During the study, participants of childbearing potential must have a negative urine or serum pregnancy test result within 72 hours before dosing on Day 1 of each cycle during treatment prior to dosing.

- If a menstrual period is delayed, absence of pregnancy in participants of childbearing potential must be confirmed by a negative urine or serum pregnancy test.
- Pregnancy tests may also be repeated during the study as per request of IRB or if required by local regulations.

EOT: At EOT, a urine or serum pregnancy test is required in participants of childbearing potential.

- m. All responses, including PD, must be confirmed by central laboratory evaluation. If the start of a cycle is delayed, serum M-protein and serum FLCs are to be collected for central laboratory analysis if not previously sent within the preceding 10 days. If a patient has collected a 24-hour urine sample and brought it to a visit, the sample should be sent for central laboratory analysis of urine M-protein even if not on Day 1 of a cycle.
- n. Screening levels for Part 3 must be ≥500 mg/dL. To be repeated at baseline (C1D1) if screening sample was taken more than 7 days before C1D1.
- o. Sample to be collected at any time on Day 2 of the cycle.
- ^{p.} Urine M-protein 24-hour urine sample required while on treatment and during follow-up. To be repeated at baseline (C1D1) if screening sample was taken more than 7 days before C1D1.
- 9. Serum FLC to be repeated at baseline (C1D1) if screening sample was taken more than 7 days before C1D1.
- Immunofixation in serum and urine is required for patients evaluated for CR; see Sections 9.3.10.6. To be repeated at baseline (C1D1) if screening sample was taken more than 7 days before C1D1.

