7.4 Demographic and Other Baseline Characteristics

All demographics and baseline characteristics will be summarized by safety analysis set in Part 1 escalation cohorts and Part 2 expansion cohorts and by full analysis set in Part 3 extension cohorts.

Demographics

Demographic data to be evaluated will include age, sex, race, ethnicity, height, and weight.

Stratification factors (Part 3 only)

- Type of Myeloma
 - IgA
 - Other
- Cytogenetic
 - High risk [(del17, t(4;14) and/or t(14;16)]
 - Standard risk

Disease characteristics:

- Years since initial diagnosis [(date of first dose – date of diagnosis) / 365.25)].
- Type of Myeloma
 - IgG, IgA, IgD, IgM, Biclonal (if known, otherwise summarize with Light chain below).

- Light Chain Kappa, Light Chain Lambda, Light chain Biclonal, Light Chain unknown.
- Measurable disease
 - Measurable by both SPEP (baseline serum M-protein ≥ 0.5 g/dL) and UPEP (baseline urine M-protein ≥ 200 mg/24 hr)
 - Measurable by SPEP only
 - Measurable by UPEP only
 - Measurable by FLC only (met all three criteria below):
 1. Involved either Kappa or Lambda free light chain level at baseline ≥ 10 mg/dL;
 2. and FLC ratio (Kappa FLC/Lambda FLC) is abnormal (serum FLC ratio > 1.65 or < 0.26)
 3. and not measurable by SPEP or UPEP
 - Non-measurable (not measurable by SPEP, UPEP, or FLC)
- Durie-Salmon Stage.
- International Staging System (ISS) at initial diagnosis.
- International Staging System (ISS) at study entry.
- Evidence of Lytic Bone Disease at initial diagnosis.
- Evidence of Extramedullary Disease at initial diagnosis.
- Eastern Cooperative Oncology Group (ECOG) performance status.

Baseline disease characteristics—laboratory values

- β_2 -microglobulin category (< 2.5 , $2.5-5.5$, > 5.5 mg/L).
- Serum albumin category (< 3.5 , ≥ 3.5 mg/dL).
- Serum creatinine category (≤ 2 , > 2 mg/dL).
- Calculated creatinine clearance category (< 30 , $30 - < 60$, $60 - < 90$, ≥ 90 mL/min).
Creatinine clearance will be calculated using the Cockcroft-Gault formulas as follows:

For male patients:

$$\text{creatinine clearance} = \frac{(140 - \text{Age[yrs]}) \times \text{weight[kg]}}{72 \times (\text{serum creatinine [mg/dL]})}$$

For female patients multiply by 0.85.

- Hemoglobin (g/L).
- Platelet count (10^9 /L).
- Absolute neutrophil count (10^9 /L).
- Lactate dehydrogenase (LDH) $>$ Upper limit of normal (ULN).

Baseline Bone Marrow Evaluation

- Baseline bone marrow aspirate/biopsy performed and adequate for interpretation.

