7.8.2.4 Subgroup Efficacy Analysis

For the primary endpoint ORR by IRC assessment, subgroup analysis will be performed in the following selected subgroups.

Subgroups	Categories
Age group (at screening)	e.g. 18 to <70 ; ≥ 70
Gender	Male; female

Race	White; Black; Asian; Other
Type of myeloma	IgA; IgG; light chain only
Cytogenetics risk	High risk [defined as 17p-, t(4;14) and/or t(14;16)]; complementary standard risk (non-high risk) Expanded high risk [defined as High risk and/or 1q21 amplification/gain]; complementary standard risk (non-expanded high risk)
Prior treatment	Anti-CD38 in last line of therapy; IMiD in last line of therapy; Recently approved agents (Selinexor, Anti-BCMA CAR-T, belantamab); Bispecific T-cell engagers; Anti-BCMA exposed; Anti-BCMA exposed (CAR-T); Anti-BCMA exposed (ADC); Anti-BCMA exposed (Bispecific T-cell engagers); Penta exposed.
Number of prior lines of therapy	≤4, >4
Refractory to prior anti-cancer therapy	Anti-CD38 monoclonal antibody; CAR-T; IMiD (Lenalidomide, Pomalidomide, Thalidomide); Proteasome Inhibitor; Triple refractory (IMiD, PI, and anti-CD38); Penta refractory (Bortezomib, Carfilzomib, Lenalidomide, Pomalidomide and anti-CD38); Anti-BCMA refractory; Triple refractory and bispecific T-cell engager exposed.

In the subgroup analysis, ORR will be presented using forest plot within each treatment arm for the following categories: age, gender, race, type of myeloma, cytogenetic risk group, prior treatment, number of prior lines of therapy, and refractory to prior anti-cancer therapy. Other subgroups may be explored if data permits, but not required by this SAP. If the percentage of subjects is small within a particular subgroup, then the subgroup categories may be refined prior to the primary analysis of Part 3 extension.

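### Footnote n to the Part 3 screening schedule (Protocol Appendix A Table 12) states a serum-only threshold that conflicts with inclusion criterion 3

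*Protocol*

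**What the plan says.** **Footnote.** The Part 3 screening schedule (Protocol Appendix A Table 12) has a row labelled "Serum M-protein m, n (central analysis"). Footnote n begins "Screening levels for Part 3 must be ≥500 mg/dL". It then asks for the test to be repeated on Cycle 1 Day 1 if the screening sample is more than 7 days old. It mentions neither urine nor FLC and does not refer to the eligibility list.

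**Eligibility list.** Protocol Section 7.1, criterion 3, covers Parts 2 and 3 and opens "Measurable disease defined as one of the following". Item a is serum M-protein at 500 mg/dL or more. Item b is "Urine M-protein ≥200 mg/24 hours". Item c is "Serum free light chain (FLC) assay with involved FLC level ≥10 mg/dL (≥100 mg/L) provided serum FLC ratio is abnormal".

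**Study summary.** Protocol Section 2.0 has the same structure and names Part 3: "Patients in the Part 2 expansion and Part 3 extension cohorts must have measurable disease defined as one of the following".

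**Analysis plan.** SAP Section 7.4 has baseline categories for "Measurable by UPEP only" and for FLC only. SAP Section 7.8.2.4 lists the myeloma-type subgroups for IRC-assessed ORR as "IgA; IgG; light chain only".

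**The concern.** The footnote uses mandatory wording and is specific to Part 3. A reader at a site or at the central laboratory could take it as a stricter Part 3 rule added to criterion 3.

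If it were applied that way, patients whose disease is measurable only in urine or by FLC would fail screening although Section 7.1 admits them. Sites could also differ in which text they follow. At stake are consistent eligibility across sites, the population to which the primary ORR applies, and the numbers in the analysis groups that exist for these patients. Protocol Section 14.2 allows no exemptions from the inclusion and exclusion criteria, so sites need a single unambiguous rule.

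**Working it through.** The plan gives no figure on this point, so there is none to reproduce. The check compares two eligibility rules.

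**1. Is the footnote value the same as criterion 3a?** 500 mg/dL ÷ 1000 = 0.5 g/dL, and 0.5 g/dL × 10 = 5 g/L. It is. The footnote restates item a without items b and c.

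**2. Where do the rules differ?** Let S, U and F mean measurable by serum M-protein, urine M-protein and FLC. Section 7.1 accepts S or U or F. Footnote n, read literally, requires S.

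| S | U | F | Section 7.1 | Footnote n |
|---|---|---|---|---|
| no | no | no | fail | fail |
| no | no | yes | **eligible** | **fail** |
| no | yes | no | **eligible** | **fail** |
| no | yes | yes | **eligible** | **fail** |
| yes | no | no | eligible | pass |
| yes | no | yes | eligible | pass |
| yes | yes | no | eligible | pass |
| yes | yes | yes | eligible | pass |

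Section 7.1 accepts 7 of the 8 patterns and footnote n accepts 4. The 7 − 4 = 3 in dispute are FLC only, urine only, and urine plus FLC without serum. These are counts of patterns and say nothing about how many patients fall in each.

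**3. Which text fits the rest of the plan?**
- Protocol Appendix F defines partial response on the FLC difference when neither serum nor urine M-protein is measurable. It also has FLC rules for complete and very good partial response.
- SAP Section 7.4 keeps urine-only and FLC-only baseline categories, and the FLC-only category requires that the patient is not measurable by serum or urine.
- SAP Tables 1 and 2 (PFS and TTP censoring) count a urine or FLC measurement alone as an adequate baseline.
- The Part 3 waterfall plot in SAP Section 7.8.2.1 falls back to urine and then to FLC when serum is not available.
- SAP Section 7.8.2.4 plans the light-chain-only subgroup.

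All of these agree with criterion 3. Only footnote n does not.

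**4. Is the Part 3 design calculation affected?** The success rule is at least 33 responders among 118 treated patients per arm (Protocol Appendix H). The exact binomial tail P(X ≥ 33 | n = 118) is 0.0235 at a true ORR of 20% and 0.957 at 35%, before any futility look. This agrees with the stated one-sided 0.025 and power above 90%. The calculation uses treated patients only, so screening failures do not enter it.

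**The case against.** The strongest reply is that Section 7.1, not a schedule footnote, decides who is enrolled. Section 9.3 refers the reader to Appendix A for the timing of assessments, Table 12 has its own eligibility row, and the rest of footnote n is about repeat sampling. On this view the sentence is a stray copy of criterion 3a that a careful site would ignore.

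Much of this stands. Section 7.1 is the formal list, and nothing in the documents shows that a site screened from the footnote. It does not remove the point, for two reasons. Footnotes to the same schedule do carry exclusions: the hepatitis footnote states who is excluded. And the matching footnote k in the Parts 1 and 2 schedule has the repeat-sampling instruction but no threshold, so the Part 3 sentence can look deliberate.

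A reader might infer more than the documents support:
- **That Part 3 excludes urine-only and FLC-only patients.** Section 7.1 and the study summary say the opposite. Loss occurs only if the footnote is applied literally.
- **That a fraction of the 118 per arm is lost.** The documents give no share. Patients who fail screening are never among the 118, because enrolment runs to that target. The possible effects are on case mix and on the number screened.
- **That Table 13 has the same fault.** The footnotes are printed once for both tables, but marker n is not on the Table 13 serum M-protein row.
- **That an emptied subgroup would damage the primary claim.** The subgroup analysis carries no success criterion, and SAP Section 7.8.2.4 already allows small categories to be refined before the primary analysis.

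**Conclusion.** The inconsistency is certain. Footnote n to Table 12 states a serum-only threshold that conflicts with criterion 3 and the study summary, and the rest of the plan indicates that the footnote is the text in error.

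The consequence is conditional. If a site or the central laboratory applied the footnote literally, eligible patients in three measurability patterns could be failed. The population behind the primary ORR would then lean towards serum-measurable disease, and the light-chain-only subgroup and the urine-only and FLC-only categories would be thinned. Whether this happened, and for what share of patients, cannot be determined from the documents.

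The planned sample size is unchanged, as is power at any given true ORR. Whether the true ORR differs by type of measurable disease is not stated, so no direction of effect on the estimate is claimed. The point merits correction because it touches eligibility and costs almost nothing to put right. It is not a flaw in the design.

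**What to change.** Reconcile footnote n with criterion 3 in one of two ways:
- delete the threshold sentence and keep the repeat-sampling instruction; or
- limit the sentence to patients who qualify by serum M-protein, and refer to criterion 3 for urine and FLC.

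If the sponsor did intend a serum-only rule for Part 3, the texts to change are Section 7.1, the study summary and the SAP categories listed above. Nothing in the documents suggests that intention.

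If enrolment has closed, use the summary of screen-failure reasons already planned in SAP Section 7.3. Look for Part 3 patients failed on serum M-protein alone, check whether they met criterion 3 by urine or FLC, and report the count.

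The cost is one footnote edit, a clarification to sites and the central laboratory and, if enrolment is complete, a review of screening records. No analysis, boundary or sample size needs to change.
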